# 16.3. Exploratory Efficacy

Exploratory efficacy endpoints are defined in Section 16.

#### 16.3.1. Exploratory Efficacy Variables and Derivations

Exploratory efficacy endpoints are:

- The proportion of participants achieving symptomatic remission at Weeks 2, 4, 8
- The proportion of participants achieving complete symptomatic remission at each study visit (Weeks 2, 4, 8, 12)
- The proportion of participants achieving noninvasive clinical response at each study visit (Weeks 2, 4, 8, 12)
- The proportion of participants achieving symptomatic response at each study visit (Weeks 2, 4, 8, 12)
- The proportion of participants with remission and response using TMS at Week 12
- The proportion of participants with histologic improvement at Week 12 (as defined by the Geboes Index, Robarts Histopathology Index, and Nancy Histologic Index)
- The proportion of participants with histologic remission at Week 12 (as defined by the Geboes Index, Robarts Histopathology Index, and Nancy Histologic Index)
- The proportion of participants with improvement in extraintestinal manifestations (EIMs) at Week 12 in participants with EIMs at baseline

#### 16.3.2. Missing Data Methods for Exploratory Efficacy Variables

All participants with missing data, regardless of reason for missingness, will be considered as non-responders. The intercurrent events that are considered in the primary efficacy analysis will be handled similarly for the exploratory efficacy endpoints, as specified in Section 16.1.2.

#### 16.3.3. Analysis of Exploratory Efficacy Variables

All proportion-based endpoints will be analysed as described in Section 16.1.3 for the mFAS with Baseline MMS 5 to 9. The pairwise Spearman's rank correlation coefficients among the 3 histological scoring indices will also be presented by treatment group.

No multiplicity adjustments will be made.

Document: \quintiles.net\enterprise\Apps\sasdata\SASb\SAS\Arena\APD334\RZA28116\Biostatistics\Documenta

tion\SAP\503-Final SAP v2.0\APD334-203\_SAP\_Final v2.0-20231120\_clean.docx

Author: PPD Version Number: 2.0

Version Date: 20Nov2023

Template No.: CS\_TP\_BS016 Revision 7 Reference: CS\_WI\_BS005

Effective Date: 01Nov2021

Page 38 of 70

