Participants who discontinue treatment prematurely, regardless of the reason, should be instructed to return for an ET visit within 7 days of the last administration of study treatment ([Table 6](#)) and complete all of the ET assessments. If a participant discontinues due to pregnancy, they are not required to complete the endoscopy. If the ET visit is within 4 weeks of the last sigmoidoscopy and biopsy, these procedures do not need to be repeated.

If the ET visit is ≥ 2 weeks after the last administration of study treatment, the 2-Week Follow-Up visit is not required; however, the 4-Week Follow-Up visit should be scheduled and completed. If the ET visit is ≥ 4 weeks of the last dose of study treatment, the 4-Week Follow-Up visit is not required unless the ALC is not within normal limits.

If treatment discontinuation is considered an adverse event, refer to Section [9.9.8.3.](#) for AE/SAE reporting guidance.

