5.2. Discontinuation from the Study

Participants may be discontinued from the study at any time for any of the following reasons:

- Withdrawal by participant
- Deviation/noncompliance with the study protocol that in the judgement of the Investigator and/or Medical Monitor the participant should not continue study treatment
- Study termination by Sponsor
- Lost to follow-up
- Death
- Other

A participant may withdraw from the study at any time for any reason without prejudice to their future medical care by the physician or at the institution. If a participant withdraws consent, no further evaluation should be performed, and no additional data should be collected. The Sponsor may retain and continue to use any data collected before such withdrawal of consent. The Investigator should make a reasonable attempt to document the specific reason why consent was withdrawn.

In the event that a participant fails to attend any follow-up visits, all reasonable efforts will be made to contact the participant to ensure that he/she is in satisfactory health. All contacts and contact attempts must be documented in the participant's file.

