9.4.2.1.3. Study Treatment Discontinuation Related to Postdose Cardiac Monitoring

A complete list of reasons for study treatment discontinuation is provided in Section 5.1. Reasons for study treatment discontinuation specific to postdose cardiac monitoring are provided in Table 4. The Medical Monitor should be contacted before discontinuing a participant.

Table 4: Discontinuation of Study Treatment Related to Postdose Cardiac Monitoring

Reasons for Study Treatment Discontinuation Related to Postdose Cardiac Monitoring ^a

Participants who have a cardiovascular treatment-related symptomatic event (eg, chest pain, dizziness, palpitations, lightheadedness, shortness of breath, or syncope) associated with reduction of the heart rate or associated with clinically relevant 12-lead ECG changes at any time during the 4-hour monitoring period on Day 1 or Day 2 (as applicable).Participants who have not met the discharge criteria on Day 1 after ≥ 4 hours of extended monitoring, or Day 2 by 4 hours postdose.

^a All treatment discontinuations should be discussed with the Medical Monitor.

ECG, electrocardiogram

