# 5.5. Modified Full Analysis Set (mFAS)

The mFAS will consist of all randomized participants who receive at least 1 dose of study treatment and have a Baseline and at least 1 post-randomization measurement. Participants will be summarized by treatment to which they were randomized, regardless of treatment actually received. Note that the mFAS can vary with endpoints since some participants may have the needed data for inclusion in the mFAS for some endpoints but others may not.

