# 8.3. Missing Data

Missing adverse event (AE) relationship to study treatment and AE seriousness will be imputed as described in Section 18.1.1.2 and Section 18.1.3, respectively. Partial or missing AE start dates, concomitant medication (CM) start dates, and hospitalization dates will also be imputed as described in APPENDIX 2. No other missing safety data will be imputed.

Missing efficacy data will be handled as described in Sections 16.1.2, 16.2.2, 16.3.2. In the primary analysis of the primary endpoint and main analyses of all binary responder-type endpoints, all participants with missing data, regardless of reason for missingness, will be considered as non-responders. In the main analysis of continuous or score endpoints, such as biomarker measures and health-related quality of life measures, participants with missing data will be analysed with their observed data only, a mixed-effect model with repeated measures or analysis of covariance (ANCOVA).

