# 17. HEALTH-RELATED QUALITY OF LIFE (HRQOL) AND HEALTHCARE RESOURCE UTILIZATION ANALYSIS

Subject-reported HRQoL instruments will be electronically captured and used in support of the efficacy outcomes. All HRQoL are administered at Baseline and Week 12. The HRQoL analyses will be performed using the mFAS with Baseline MMS 5 to 9.

All HRQoL endpoints will be analyzed using an ANCOVA for the change from Baseline, with a factor for treatment and a covariate of the corresponding HRQoL Baseline value.

Healthcare resource utilization endpoints, ie, the proportion of concomitant UC-related hospitalizations and the proportion of concomitant UC-related surgeries, including colectomy, will be analyzed as described in Section

Document: \\quintiles.net\enterprise\Apps\sasdata\SASb\SAS\Arena\APD334\RZA28116\Biostatistics\Documenta

tion\SAP\503-Final SAP v2.0\APD334-203\_SAP\_Final v2.0-20231120\_clean.docx

Author: PPD Version Number: 2.0

Version Date: 20Nov2023

Template No.: CS\_TP\_BS016 Revision 7 Reference: CS\_WI\_BS005

Effective Date: 01Nov2021

Page 39 of 70

16.1.3 for the FAS with Baseline MMS 5 to 9.

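### Exploratory responder endpoints are analysed only in the mFAS, so a participant with no post-baseline biopsy can leave the histologic denominators instead of counting as a nonresponder

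*SAP*

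**What the plan says.** SAP 16.3.2 sets the missing-data rule for the exploratory endpoints: "All participants with missing data, regardless of reason for missingness, will be considered as non-responders". It also carries over the intercurrent-event handling of 16.1.2, under which four event types give a known nonresponse. SAP 8.3 states the same rule more widely, for the primary analysis and the "main analyses of all binary responder-type endpoints, all participants with missing data, regardless of reason for missingness, will be considered as non-responders".

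SAP 16.3.3 then fixes the analysis set: "All proportion-based endpoints will be analysed as described in Section 16.1.3 for the mFAS with Baseline MMS" 5 to 9. It names no other set. SAP 5.5 restricts the mFAS to randomized, dosed participants who "have a Baseline and at least 1 post-randomization measurement", and notes that membership can differ from one endpoint to another according to the data available.

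Six of the exploratory endpoints are histologic: improvement and remission at Week 12, each by the Geboes, Robarts and Nancy indices. Protocol 9.8.1.1, 9.8.1.2 and Table 6 schedule biopsies only at the screening endoscopy and at the Week 12/ET endoscopy.

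**The concern.** Nonresponder imputation can act only on participants who are in the analysis set. For an endpoint with a single scheduled post-baseline assessment, a rule requiring at least one post-randomization measurement removes the participants whose only assessment never took place. The plan says they are failures, and the set definition takes them out of the denominator.

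This is selection after randomization, and the reasons for early dropout may differ by arm. Protocol 1.3 lists first-dose bradycardia and AV block among events reported with the S1P class, so Day 1 or Day 2 discontinuations could fall more on etrasimod and raise its rates. Dropout for lack of efficacy could fall more on placebo and act the other way.

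The exploratory endpoints have no FAS analysis to compare with. The FAS repeats in SAP 16.1.4, 16.2.4 and Table 3 cover only the primary and secondary endpoints. The disposition tables in SAP 10.1 would show set sizes and missing endoscopies, which makes the loss visible but does not correct it.

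**Working it through.** The documents give no figure on this point, so there is none to reproduce. The check has three parts.

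**1. Can a dosed participant have no post-baseline biopsy under the protocol?** Yes, by several routes.

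- *The ET waiver.* Protocol 5.1: "If the ET visit is within 4 weeks of the last sigmoidoscopy and biopsy, these procedures do not need to be repeated". The last procedure can be the screening one. Table 6 allows about 5 to 12 days for the central read, which suggests a screening endoscopy between Day -12 and Day -5. SAP 6.1 has no Day 0, so Day -12 plus 28 days is Day 17, and Day -5 plus 28 days is Day 24. ET visits up to Day 17 to 24 therefore need no biopsy.
- *Cardiac discontinuation.* Protocol Table 4 stops treatment for participants "who have not met the discharge criteria on Day 1 after" at least 4 hours of extended monitoring, or on Day 2 by 4 hours postdose. The ET visit is due within 7 days of the last dose: Day 1 + 7 = Day 8, or Day 2 + 7 = Day 9. Day 9 minus 28 days is Day -20, so any screening endoscopy from about Day -20 onward waives the ET biopsy.
- *Withdrawal of consent.* Protocol 5.2: "If a participant withdraws consent, no further evaluation should be performed, and no additional data should be collected".
- *Pregnancy.* Protocol 5.1 does not require the endoscopy.

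**2. Where does such a participant go?**

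| Endpoint | Set | Participant with no post-baseline biopsy |
|---|---|---|
| Mucosal healing, secondary (ES and Geboes < 2.0) | FAS, MMS 5 to 9 (SAP 16.2.3) | Nonresponder |
| Histologic remission, exploratory (Geboes < 2.0) | mFAS, MMS 5 to 9 (SAP 16.3.3) | Outside the endpoint's mFAS |
| Other five histologic endpoints | mFAS, MMS 5 to 9 | Outside the endpoint's mFAS |

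Imputation still works in one case. If an ET biopsy was taken before the Week 12 window opens at Day 66 (SAP Table 2), the participant has a post-randomization measurement, stays in the mFAS and counts as a nonresponder.

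SAP 5.5 leaves two matters open. It does not say whether earlier SF/RB diary scores are enough for the two TMS endpoints, which also need the endoscopic and PGA components. It does not say whether a known nonresponse under 16.1.2 satisfies the measurement requirement when no biopsy exists.

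**3. Size.** Let p be an arm's responder rate in the FAS under nonresponder imputation, and u the share with no post-baseline measurement. Excluded participants are all nonresponders in the FAS, so the numerator is unchanged:

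mFAS rate = p / (1 - u)

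The multiplier is 1/0.95 = 1.05 at u = 5%, 1/0.90 = 1.11 at 10% and 1/0.80 = 1.25 at 20%. One excluded participant multiplies the rate by 32/31 = 1.03 in an arm of 32 (the planned size), or by 16/15 = 1.07 in an arm of 16 (assumed, because the study stops early).

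With assumed FAS rates of 30% active and 10% placebo, a difference of 20.0 points:

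| u active | u placebo | mFAS active | mFAS placebo | Difference (points) |
|---|---|---|---|---|
| 0% | 0% | 30.0% | 10.0% | 20.0 |
| 10% | 10% | 30/0.90 = 33.3% | 10/0.90 = 11.1% | 22.2 |
| 20% | 5% | 30/0.80 = 37.5% | 10/0.95 = 10.5% | 27.0 |
| 5% | 20% | 30/0.95 = 31.6% | 10/0.80 = 12.5% | 19.1 |
| 8% | 0% | 30/0.92 = 32.6% | 10.0% | 22.6 |

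The last row uses the only related figures in the documents. Protocol 3.2 reports that in the earlier Phase 2 study TEAEs led to treatment discontinuation in 8.0% on 2 mg and 0% on placebo. The row assumes that every such participant had no biopsy, and it leaves out all other reasons for dropout.

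**The case against.** The strongest reply is that there is no contradiction. A missing-data rule always operates within an analysis set, and SAP 16.1.4 and 16.2.4 combine nonresponder imputation with the mFAS explicitly. The protocol lists the mFAS among the sets that may be used and assigns none to exploratory endpoints, and SAP 17 uses the mFAS for HRQoL. That shows the combination was deliberate. But in 16.1.4 and 16.2.4 the mFAS run supplements a FAS analysis, whereas in 16.3.3 it is the only one.

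Second, mucosal healing uses the same biopsy and the same Geboes cut-off and is reported in both FAS and mFAS, so the reader gets some indication of the effect. This is partial cover. Mucosal healing also requires the endoscopic component, and it says nothing about histologic improvement or the Robarts and Nancy indices.

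Third, the effect depends on an unsettled reading of 5.5. If any post-randomization efficacy value qualified, or if a known nonresponse counted, many of these participants would stay in. That is fair. The note that the mFAS varies by endpoint points the other way, and the uncertainty means two programmers could produce different denominators.

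Fourth, the route is narrow and the 20% share has no support in the documents. The waiver is permissive and covers only early ET visits, and Protocol 1.3 reports no clinically significant vital-sign or ECG concerns in the earlier etrasimod studies. This stands as a limit on the likely size. It does not remove the selection.

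Fifth, no problem has been shown for the diary endpoints measured at four visits. That also stands; including them in the fix is for consistency.

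**Conclusion.** The concern holds. As written, SAP 16.3.3 can remove from the histologic denominators participants whom 8.3 and 16.3.2 call nonresponders, and the protocol's own waivers make such participants possible. The distortion is a factor of 1/(1-u) in each arm. On the assumed 30% vs 10%, the difference ranges from 19.1 to 27.0 points across the shares shown, and is 22.6 when tied to the earlier study's 8.0% and 0%. It can move in either direction and is zero if everyone has a post-baseline biopsy. All rates and shares are assumptions, and the exclusion rests on the endpoint-specific reading of 5.5.

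The consequence is limited to reported exploratory rates, differences, odds ratios and confidence intervals. No test is planned, and the primary and secondary FAS analyses are untouched. It is worth correcting because the correction is cheap.

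**What to change.** In SAP 16.3.3, replace the mFAS with Baseline MMS 5 to 9 by the FAS with Baseline MMS 5 to 9 for the exploratory responder endpoints. Keep the restriction to participants with EIMs at baseline for the EIM endpoint. No other section needs to change.

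This brings the exploratory endpoints into line with the primary and secondary ones. Symptomatic remission, for example, would then use one population at Weeks 2, 4, 8 and 12. It also matches the healthcare utilization proportions in SAP 17, which already follow "16.1.3 for the FAS with Baseline MMS 5 to 9". If outputs have already been produced, add the FAS version and identify it in the CSR as SAP 4.2 requires for unplanned analyses.

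The cost is one phrase and one population flag in programming. Where participants lack a post-baseline measurement, the reported exploratory rates will be slightly lower.

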#### 16.4. Efficacy-Related Biomarkers

Value and change from Baseline in level of fecal calprotectin (FCP), hs-CRP, and lymphocyte counts at protocolspecified visits will be summarized by visit and treatment for the FAS with Baseline MMS 5 to 9. Additionally,
percent change from Baseline in lymphocyte counts will also be summarized. Change from Baseline in these
biomarkers will also be analysed using a mixed-effect model with repeated measures (MMRM), with factors for
treatment, visit, treatment by visit interaction, and a covariate of the corresponding Baseline value. Unstructured
covariance will be used. If there is a convergence issue in fitting the unstructured covariance, a heterogeneous
Toeplitz, heterogeneous autoregressive (1), autoregressive (1), or compound symmetry covariance structure will be
used. The same model will be fit to the percent change from Baseline in lymphocytes. LS means, SEs, and CIs by
visit will be reported.

Additionally, the following summaries will be provided for biomarker data:

- Line plots over time for LS mean and SE for the following laboratory assessments:
  - Change from Baseline in lymphocytes
  - Percent change from Baseline in lymphocytes
  - Change from Baseline in hs-CRP
  - Change from Baseline in FCP

The exploratory efficacy-related biomarker analyses for immunophenotyping and proteomics will be described in a separate biomarker analysis plan.

# 17. HEALTH-RELATED QUALITY OF LIFE (HRQOL) AND HEALTHCARE RESOURCE UTILIZATION ANALYSIS

Subject-reported HRQoL instruments will be electronically captured and used in support of the efficacy outcomes. All HRQoL are administered at Baseline and Week 12. The HRQoL analyses will be performed using the mFAS with Baseline MMS 5 to 9.

All HRQoL endpoints will be analyzed using an ANCOVA for the change from Baseline, with a factor for treatment and a covariate of the corresponding HRQoL Baseline value.

Healthcare resource utilization endpoints, ie, the proportion of concomitant UC-related hospitalizations and the proportion of concomitant UC-related surgeries, including colectomy, will be analyzed as described in Section

Document: \\quintiles.net\enterprise\Apps\sasdata\SASb\SAS\Arena\APD334\RZA28116\Biostatistics\Documenta

tion\SAP\503-Final SAP v2.0\APD334-203\_SAP\_Final v2.0-20231120\_clean.docx

Author: PPD Version Number: 2.0

Version Date: 20Nov2023

Template No.: CS\_TP\_BS016 Revision 7 Reference: CS\_WI\_BS005

Effective Date: 01Nov2021

Page 39 of 70

16.1.3 for the FAS with Baseline MMS 5 to 9.

#### 17.1. Variables and Derivations

#### 17.1.1. Ulcerative Colitis Patient-Reported Outcomes Signs and Symptoms

The Ulcerative Colitis Patient-Reported Outcomes Signs and Symptoms (UC-PRO/SS) is a 9-item daily diary designed to quantify the effects of treatment on patient-reported signs and symptoms of UC. Two separate weekly average scores will be calculated, one for bowel signs and symptoms score (6 items), and the other for abdominal symptoms (3 items). The higher the score, the worse the symptoms. The UC-PRO/SS scores and change from Baseline at Week 12 will be evaluated. Details about scoring rules can be found in APPENDIX 3.

#### 17.1.2. 36 Item Short Form Health Survey, version 2

The 36-Item Short Form Health Survey (SF-36) is a 36-item, subject-reported survey of subject health. The SF-36 consists of 36 questions measuring 8 health domains: physical functioning, bodily pain, role limitations due to physical problems, role limitations due to emotional problems, general health perceptions, mental health, social function, and vitality. The subject's responses are solicited using Likert scales that vary in length, with 3 to 6 response options per item. The SF-36 will be scored using 2 overall summary scores; physical component summary and mental component summary scores. A higher score indicates better health status.

The Physical Component Summary Score (norm-based), the Mental Component Summary Score (norm-based), 8 domain subscores (0 to 100 based), and the SF-6D health utility index score are derived by Optum and integrated into the SF-36 eCRF. Details about scoring rules and derivations of domain/component scores can be found in APPENDIX 4.

#### 17.1.3. UC-Related Hospitalizations and Surgeries

The UC-related hospitalizations are captured on the Adverse Events eCRF. The UC-related surgeries, including colectomy, are captured on the Concomitant Non-Drug Treatment eCRF. Blinded review of AE preferred terms will be performed to determine UC-related hospitalizations.

\\quintiles.net\enterprise\Apps\sasdata\SASb\SAS\Arena\APD334\RZA28116\Biostatistics\Documenta Document:

tion\SAP\503-Final SAP v2.0\APD334-203\_SAP\_Final v2.0-20231120\_clean.docx

Version Number: 2.0 Author: PPD

> Version Date: 20Nov2023

Template No.: CS\_TP\_BS016 Revision 7 Reference: CS WI BS005

Effective Date: 01Nov2021

Page 40 of 70

#### 17.2. Missing Data Methods

Missing data will not be imputed for HRQoL endpoints.

#### 18. SAFETY OUTCOMES

All outputs for safety outcomes will be based on the SS. There will be no statistical comparisons between the treatment groups for safety data, unless otherwise specified.

#### 18.1. Adverse Events

AEs will be coded using MedDRA (v24.1 or higher). The version used to code AEs will be displayed in the analyses. Treatment emergent adverse events (TEAEs) are defined as AEs that started or worsened in severity on or after the first dose of study treatment.

Refer to APPENDIX 2 for handling of partial dates for AEs for the purpose of assigning treatment-emergent flags. In the case where it is not possible to define an AE as treatment emergent or not, the AE will be classified as treatment emergent.

